Title: Improving Function in Older Veterans With Hospital-Associated Deconditioning

NCT: 02696382

Version Date: 05.23.2022

Protocol #: 15-1571 Project Title: Improving function in older Veterans with hospital-associated deconditioning Principal Investigator: [name], PT, PhD Version Date: 05.23.2022

I. Hypotheses and Specific Aims:

Hospitalization with subsequent deconditioning (hospital-associated deconditioning) is a common and profound contributor to functional decline in older adults.¹⁻³ Skeletal muscle weakness and atrophy are commonly observed in older adults with deconditioning after a hospitalization,^{2,4,5} leading to development of chronic functional deficits. This is especially concerning for elderly Veterans, a population who has lower physical function⁶ and more comorbidities^{7,8} at baseline than the general older adult population, and therefore may be at even higher risk for developing disability in activities of daily living (ADLs) after hospitalization.⁹ Thus, our research has the following aims

Specific Aim 1: To determine if PHIT training, initiated upon discharge from an acute care hospital, is as safe and more effective than UC in promoting sustained gains in physical function for older Veterans.

Hypothesis 1.1: There will be greater improvements in gait speed (primary outcome), Short Physical Performance Battery Scores (SPPB), modified Physical Performance Test (mPPT), Timed Up and Go test (TUG), grip strength, and knee extensor muscle strength in the PHIT group compared to the UC group at 60 days following hospital discharge, without increasing adverse events. Benefits of PHIT will be apparent at the end of intervention (30 days), will increase further at 60 days (primary endpoint), and will persist at 90 and 180 days.

Specific Aim 2: To determine if PHIT intervention, initiated upon discharge from an acute care hospital, improves independence in home and community mobility more than UC in older Veterans.

Hypothesis 2.1: There will be greater recovery in the PHIT group in measures of home and community mobility, as measured by the Nottingham Extended ADL Index, physical activity (PA) monitors, and the Life-Space Assessment (home and community mobility). Assessments will be performed at all time-points.

Specific Aim 3: To determine if PHIT rehabilitation, initiated upon hospital discharge, improves Veteran quality of life (QOL) & cognition, with concomitant reduction in caregiver burden compared to UC.

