The Life-Space Assessment (LSA) is a self-report measure assessing a patient's movements, extending from within the home to movement beyond a patient's town or geographic region.⁶¹ The life-space assessment is a continuous measure which can be scored from 0 (totally bedbound and dependent with all activity) to 120 (independent with community ambulation without assistance). The scores take into account both the performance of movement within and outside the home, the frequency of the movement, and the amount of assistance required. Specifically, this measure allows evaluation of actual mobility performed in the home and community, and can be evaluated for older adults across all levels of function. LSA has concurrent validity with physical function measures, as well as self-reported health and ADL disability.⁶² The Life-Space Assessment has good test-rest-reliability (ICC=0.96), and is responsive to change in community-dwelling older adults.⁶¹

Quality of Life and Caregiver Burden (Aim 3)

The Veterans RAND 12 Item Health Survey (VR-12) will be used to assess the quality of life in Veterans. The SF-12 has strong concurrent validity with well-established quality of life measures and is reliable for assessing changes in quality of life in community dwelling adults.⁶³

The Caregiver Burden Inventory (CBI) is a multi-dimensional 24-item scale with a five-point scoring system from 0 (never) to 4 (nearly always). The subscales of the CBI demonstrate strong convergent validity with caregiver depression, caregiver satisfaction, and number of caregiver tasks.³¹

Adverse Events Reporting Script will be used to assess any adverse events (e.g. ER visit(s), hospitalization(s), major illness/injury) which occurred since the last study visit and whether the participant is completing their exercises. The AE script will be administered 7 times, once at each of the 5 study visits, and once during each of 2 phone calls.

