D2.5. Intervention: Patients in the PHIT exercise group will receive between 10 and 12 PT visits in their home (45-60 min/session). Data from 3 local home health agencies indicated that the average number of physical therapy visits per episode of care was 8.5 (Agency 1), 7.8 (Agency 2), and 8.6 (Agency 3). Furthermore, the average number of PT visits from the preliminary data for the PHIT and UC groups were 9.8 and 8.4 visits, respectively. Therefore, we chose to target 10-12 PT visits for the proposed study to operate within a reasonable range of the current standards of care and maximize the benefits of the PHIT intervention. Our preliminary data suggest that this frequency of visits (10-12 visits over 4 weeks) will produce neuromuscular and physiological changes that will translate to improved function. Patients in the PHIT group will receive 3-4 visits per week for the first two weeks and 2 visits per week, on non-consecutive days for the remaining 2 weeks (total=10-12 visits). The intervention will consist of progressive resistance exercises for the lower extremity with a portable training device (Shuttle Mini-Press), a motor control-based program of gait/balance training, and ADL training—all designed to

improve mobility (see Table 2; Appendix). PHIT participants will also receive specific written nutritional education to emphasize the importance of increasing protein intake by 15 grams/day to support participation in the high intensity program (see Appendix).

The patients in the UC group will also receive 10-12 visits to match the PHIT group over 4 weeks. We will provide a standardized rehabilitation protocol for the UC group to perform over the 10-visit intervention period, which consists of a controlled low intensity program with activities from each of the domains included in the PHIT program (see Appendix). Both groups will also receive a standardized simple home exercise program, which will include identical exercise activities that differ only on intensity (See Appendix).

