The characteristics of the time trajectory (30, 60, 90 and 180 days of follow-up) for treatment effects will also be analyzed in secondary analyses to elucidate the mechanism and inform the

development of methods to improve long-term outcomes. The analytic methods will include maximum likelihood estimates from a repeated measures model of the mean effect at each of the measurement times.⁸⁵ The trend in means will be evaluated using a linear contrast as the summary measure of greatest interest.⁸⁶ This approach will evaluate whether there are differences in the first-order trends (slope) between intervention groups. Finally, we will estimate adverse events rates (falls, emergency department visits, nursing home days, or rehospitalizations) for each arm and compare rates between arms using a likelihood ratio test. We will additionally investigate whether training volume significantly explained additional variability in functional gains within the PHIT group using regression analysis.

Sample Size Estimates

Statistical power was estimated based on the results of a pilot study of 18 participants: 8 were randomized to PHIT, 10 to the UC interventions (results for SPPB, gait speed, and mPPT are shown in Figure 2). We observed a between group difference \pm SD in gait speed of 0.18 \pm 0.29 meters/second (m/s) in the preliminary study. Thus, a sample size of 112 patients completing the study (56/group) will provide 90% power (assuming the same pooled SD in both groups to be conservative) to detect differences at least that great. This represents 1.8 times a clinically important difference of 0.1m/s.⁴⁶ This estimate is conditional upon using a 2-sided, alpha = 0.05 level 2-group t-test.

We expect that we will consent 250 Veterans and spouses for the study, with allowance for a 25% screening failure. Screening failures that occur after consent is obtained and before enrollment in the study may include a change in medical status during hospitalization requiring a discharge to a location other than home health (e.g skilled nursing facility), a hospital re-admission which occurs after hospital discharge but prior to the baseline assessment being completed, or a failure to meet specific performance inclusion criteria (e.g. a Veteran or spouse who lacks the ability to ambulate 10 feet without at least minimal physical assistance [more than supervision or light touching for steadiness] from another person)

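### Adverse-event rates are to be compared by arm with no time window, denominator or period split, so an excess confined to the four weeks of therapy could be diluted

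*Combined protocol and SAP*

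**What the plan says.** Safety is part of Specific Aim 1, which asks whether PHIT "is as safe and more effective than UC". Hypothesis 1.1 expects better function "compared to the UC group at 60 days following hospital discharge, without increasing adverse events".

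The analysis that answers this is one sentence near the end of F. Data Analysis Plan: "we will estimate adverse events rates (falls, emergency department visits, nursing home days, or rehospitalizations) for each arm", and then "compare rates between arms using a likelihood ratio test". The sentence names four event types. It does not say over what period the rates are taken, what the denominator is, or whether the event types are combined. The time-trajectory analysis just before it is a repeated measures model of mean effects and is not stated to cover adverse events.

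On duration, D2.5 sets the same 4-week course for both arms (usual-care patients "will also receive 10-12 visits to match the PHIT group over 4 weeks"), and the Data Analysis Plan refers to a 30-day intervention period. On collection, the entry for the Adverse Events Reporting Script under Outcome Measures says "The AE script will be administered 7 times". Table 1 places those contacts at baseline and days 30, 60, 90, 120, 150 and 180, with days 120 and 150 by telephone. Each contact asks about events since the last study visit.

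**The concern.** Efficacy is analysed by time point; safety is not. Yet the safety question here depends on time. The arms differ most in delivered intensity during the supervised weeks, which are roughly one sixth of the collection period. The protocol also hopes that better function will reduce later health care use. If a training-period excess and a later reduction both occurred, a rate pooled over follow-up would average them.

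The result is meant to be used. The Background reports that home health therapists hold back from intensive work partly because they worry about injuring patients. It says that safe delivery at home has not been fully evaluated, and it expects the trial to answer the view that conservative therapy is safer. That message is mainly about the training weeks. A pooled ratio near 1 would not by itself support it. In addition, because no window is stated, the window could be chosen after the data are seen.

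**Working it through.** **The plan's own figure.** The documents give no sample size, event rate or margin for safety. The only figure to reproduce is the one for gait speed (difference 0.18 m/s, SD 0.29, two-sided 0.05, 90% power): n = 2 × (1.960 + 1.282)² × 0.29² / 0.18² = 54.6, so 55 per arm by normal approximation. By the t-test, power is 90.2% at 56 per arm. Allowing for 25% dropout, 112 / 0.75 = 149.3, in line with the planned 150. The figure holds, but it says nothing about safety.

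**Share of follow-up in therapy.** 28/180 = 15.6%; 30/180 = 16.7%.

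**Dilution.** Let *s* be the share of usual-care events that falls in the first 30 days. With equal person-time in the arms:

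RR(pooled) = s × RR(early) + (1 − s) × RR(late)

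The later ratio that brings the pooled ratio to 1 is RR(late) = (1 − s × RR(early)) / (1 − s).

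The early ratio of 2 and each value of *s* are assumptions, because the documents give no event rates by period. With no later difference:

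| Window and timing | s | Pooled RR | Later RR that would offset it |
|---|---|---|---|
| 180 days, even | 30/180 = 0.167 | 0.167 × 2 + 0.833 = 1.17 | (1 − 0.333)/0.833 = 0.80 |
| 180 days, 30% early | 0.30 | 0.60 + 0.70 = 1.30 | 0.40/0.70 = 0.57 |
| 180 days, 40% early | 0.40 | 0.80 + 0.60 = 1.40 | 0.20/0.60 = 0.33 |
| 60 days, even | 30/60 = 0.50 | 1.00 + 0.50 = 1.50 | 0 |

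Using 28 days instead of 30 in the first row gives 1.16.

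**Power in the direction of harm.** These are simulated two-sample Poisson likelihood ratio tests with 75 per arm and full follow-up. The two-sided 0.05 level is assumed, because the plan gives none for this test. Usual care is assumed to have 0.10 to 0.25 events per person in 30 days, that is 7.5 to 18.75 events, against 15 to 37.5 under PHIT if the rate doubles.

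- 0–30 day comparison: 37% to 72%.
- Pooled 180 days, no later difference: 12% to 22% with even timing; 20% to 43% with 40% of usual-care events early.
- Pooled 180 days, even timing, later RR 0.8: 2.5%, since the true pooled ratio is then 1.

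These figures are optimistic, because events cluster within people. The second pilot study reports 6 episodes in 2 usual-care participants.

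**The case against.** A reader might infer that the plan reduces safety to a single combined rate over 180 days and therefore hides training-period harm. The documents do not say that. The sentence speaks of rates, lists four event types and gives no window. Hypothesis 1.1 puts the safety clause in a sentence about 60 days, where the same assumed doubling would show as 1.5, not 1.17. What remains is that the window is undefined and, on either reading, no period is separated.

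A reader might also infer that the sponsor expects early harm. No section says so. The section on risks sees little or no added risk, the second pilot is reported as showing no increase in injury risk, and its PHIT group had no emergency visits or readmissions by 90 days. An early excess is a possibility to be examined, not a prediction of the plan.

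Full cancellation is a special case. It needs a later reduction, and at 20% it also needs evenly spread events. The Background describes the first weeks as the time of highest readmission risk. If 30% or 40% of usual-care events are early, cancellation needs a later ratio of 0.57 or 0.33, for which the documents offer no basis.

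Exposure does not stop at week 4 either. Both arms have home programmes that differ in intensity, and PHIT patients move on to unsupervised walking and exercise. A comparison of randomized arms over the whole follow-up is therefore a legitimate question, and the early window alone should not decide safety. These points limit the concern. They do not supply the missing window, denominator or early comparison.

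**Conclusion.** The gap is real and modest in form. The one between-arm safety analysis leaves the window and denominator open and plans no comparison for the training period, although the safety claim in Aim 1 bears most directly on that period.

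Dilution is conditional on pooling and on an early excess that shrinks later. Under the assumed doubling it ranges from 1.17 (180 days, even timing) through 1.40 (180 days, 40% early) to 1.5 (60 days, even timing). Offset additionally requires fewer later events under PHIT. The direction follows from the arithmetic; the size rests on assumed event timing.

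The denominator matters as well. The stopping criteria withdraw some participants after a readmission, which shortens later person-time, possibly by different amounts in the two arms. Even a 0–30 day comparison has limited power, so a non-significant test in any window would not show that PHIT is as safe as usual care.

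**What to change.** In the adverse-event sentence of F. Data Analysis Plan, state that:

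- for each listed event type, rates per person-time are compared by randomized arm in two fixed windows, the same in both arms: baseline to the day-30 contact, and the day-30 contact to day 180;
- the whole-period comparison is reported alongside;
- each comparison is given as a rate ratio with a confidence interval;
- a conclusion of equal safety will not be drawn from the whole-period comparison alone.

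The windows should follow the scheduled contacts, not the first and last therapy sessions. Session-based limits depart from intention to treat and can differ by arm: in the second pilot, therapy ended on average at 31.1 days for PHIT and 35.3 days for usual care. The price is that a few last sessions may fall after the day-30 contact.

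The change is one of wording. No new data are needed, because the script at the day-30 visit already asks about events since the previous visit. The downside is fewer events, and so wider intervals, in the 0–30 day comparison.

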produced clinically meaningful improvements strongly supporting the importance of treatment strategy, and 2) the benefits of the PHIT intervention continued past the endpoint of the intervention suggesting sustainability (~30 days). In fact, performance in the UC group worsened from 30 to 60 days (after HH physical therapy), while improvements in the PHIT group continued after intervention (30-60 days). Furthermore, though both groups had similar medical complexity, the PHIT group participants had no ER visits or re-hospitalization at 90 days, while 6 episodes (over 2 individuals) were reported in the UC group. Finally, our pilot data included an ethnically diverse group with 23% African American and 5% Hispanic or Latino participants.

[figure not shown]

Figure 2. Phase II Colorado Pilot Study outcomes for SPPB, mPPT, and 4MW (n=18). Intervention was complete, on average, by 31.1 days (PHIT) and 35.3 days (UC). Data reported as mean±SE.

Clinically meaningful improvements can be summarized as follows: A one point difference in the SPPB represents substantial meaningful change,⁴⁶ and we saw differences twice this large in our preliminary data. In fact, PHIT resulted in a 60% improvement in function at 60 days compared to only 9.7% improvement with UC. For walking speed, a 0.1m/s difference in walking speed represents substantial meaningful change,⁴⁶ and we saw differences almost twice this large in our preliminary data. In fact, 30% of patients in the PHIT group achieved >1.0m/s walking speed (threshold for independent community ambulation)⁴⁷ at 60 days; no UC group patients achieved this walking speed. Importantly, both groups received a comparable number of visits. Furthermore, these results provide evidence for the investigative team's experience managing medically complex patients using the proposed intervention strategy with favorable outcomes.

IV. Research Methods

A. Outcome Measure(s): All measures and time points for each to be assessed are summarized in Table 1. Copies of each tool are attached to this application.

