D2.3. Subject identification, recruitment, and randomization: Participants will be recruited from the Denver VAMC, UCHealth Highlands Ranch, and UCHealth Broomfield. Two hundred and fifty Veterans will be recruited (3-4 patients per month) with at least 112 expected to complete through the 60 day episode of care to accommodate for the potential re-hospitalization rate of 20-30% among home care recipients³² and drop-outs for other reasons. We had no difficulty recruiting patients for our preliminary study (3-4 patients/month). The Denver VAMC coordinates home health services for approximately 300 Veterans/month. Of these, approximately 30/month would be eligible for this study (> 55 years old; receiving home health PT services for decreased mobility after an acute hospitalization; living within the Denver metropolitan area). Therefore, recruitment of 3-4 patients/month through the Denver VAMC alone should allow us to meet our recruitment goals

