We have established the following apriori stopping criteria for removing a Veteran from the study to maintain the safety of the participant.

Participants will be withdrawn from the study by the investigators if:

a.) They are admitted to the hospital after enrollment and the study physician determines the Veteran unsafe or inappropriate for high intensity rehabilitation as defined by the inclusion/exclusion criteria

b.) They develop a new medical or psychiatric condition after enrollment which precludes participation in exercise training based on ACSM criteria or the determination of a physician, safety officer, or investigator (i.e. new cardiac diagnosis such as unstable angina, marked change in cognition, acute illness, pneumonia)

Expected Adverse and Serious Adverse Events:

The following are expected AEs and SAEs for this study: High risk behavior, e.g. drug use and/or alcohol abuse; hospitalizations due to poor functional mobility, e.g. falls; and complication from or exacerbation of current medical diagnoses and comorbidities.

Data Management Risks: As with any study, there is a risk of data breach or disclosure of study data outside the study team (e.g through accidental loss of data, theft, inadvertent electronic or paper disclosures). We will minimize these risks through the following protocol for collecting data:

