Missing Data. All patients with outcome measurements will be included in the intent-to-treat analysis. Although we will encourage patients to be fully compliant to their assigned treatment regimen and testing sessions, they will not be dropped from follow-up measurements for lack of compliance. Although statistical methods can be used to "adjust" for missing data, these methods rely on the untestable assumption that data are "missing at random" so that the effect of the missingness can be removed through statistical modeling. We will instead focus on preventing missed follow-up visits and evaluate missingness to determine whether the data are consistent with the hypothesis of missing at random or missing completely at random.

F. Data Analysis Plan:

Primary and Secondary Outcomes: The primary outcome for this study is gait speed measured 60 days following hospital discharge. Secondary outcome measures include SPPB measured at other study time points, mPPT, LSA, NEADL, VR-12, and CBI, measured at designated study time points (see Table 3). The 60 day time point is chosen for clinical relevance because it helps establish not only efficacy but also sustainability of the effects after the initial 30-day intervention period. Preliminary descriptive and graphical analyses (including boxplots, scatterplots, profile plots) will be used for data cleaning and visualization.

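### Aim 1 asks whether PHIT is as safe as usual care, but the only between-arm safety analysis is a test for a difference, with no interval to show what excess is ruled out

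*Combined protocol and SAP*

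**What the plan says.** Specific Aim 1 (section I) is to determine whether PHIT "is as safe and more effective than UC in promoting sustained gains in physical function for older Veterans". Hypothesis 1.1 expects better function "at 60 days following hospital discharge, without increasing adverse events". Both make a no-worse claim about safety.

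Section F, in the paragraph before Sample Size Estimates, lists falls, emergency department visits, nursing home days and re-hospitalisations. It plans to estimate their rates "for each arm and compare rates between arms using a likelihood ratio test". That is the whole comparative safety analysis. No margin, between-arm interval, significance level, time window or event model is given for it. The sample size rests on gait speed alone.

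On data collection, section A states: "The AE script will be administered 7 times, once at each of the 5 study visits". Two phone calls make up the rest, and Table 1 runs to day 180. On follow-up, section C allows withdrawal when "They are admitted to the hospital after enrollment and the study physician determines the Veteran unsafe or inappropriate". The Missing Data paragraph in section D says of patients that "they will not be dropped from follow-up measurements for lack of compliance".

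**The concern.** A likelihood ratio test of equal rates can provide evidence of harm. When it is non-significant, it does not show that harm is absent: a small trial can miss a material excess. The safety part of Aim 1 is a no-worse claim, and nothing else in the plan compares the arms on safety. Sections C and A cover monitoring, withdrawal and collection, none of which is a comparative criterion.

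Following the plan exactly would therefore leave the safety part of Aim 1 without an answer. This matters to the trial's purpose. Section B.5 reports that therapists avoid intensive rehabilitation partly because they fear injuring patients, and the background argues that the trial's evidence should help counter the view that conservative care is safer at home. Such a conclusion needs a statement of how large an excess the data exclude. The efficacy conclusion is not affected.

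**Working it through.** **The plan's own figure.** The only power statement is for gait speed: difference 0.18 m/s, SD 0.29, 56 per arm, two-sided 0.05. The noncentrality is 0.18/(0.29 × √(2/56)) = 0.18/0.0548 = 3.28, and the noncentral t gives 90.2% power, so the stated 90% reproduces. 112/0.75 = 149.3, rounded up to 150, or 75 per arm. There is no counterpart for adverse events, so what follows is an illustration.

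**Inputs**
- UC risk p = 20%, 25%, 30%. Section D2.3 cites a "potential re-hospitalization rate of 20-30% among home care recipients". It gives no time horizon and covers re-hospitalisation only; reading it as the proportion of UC patients affected is my assumption.
- n = 75 per arm (all enrolled) and 56 per arm (completers). Both are shown because follow-up may end early: section C permits withdrawal after an admission, and Sample Size Estimates gives re-hospitalisation as an example of a participant being lost to the study.
- Two-sided 5% level, borrowed from the gait speed calculation.
- Each event type is treated as yes/no per person. Rates that count repeat events would give other figures.

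**Step 1: power to detect a 10-point rise.** Power = Φ[(0.10 − 1.96·SE0)/SE1], with SE0 = √(2·p̄(1−p̄)/n) and SE1 = √([p1(1−p1) + p2(1−p2)]/n). For 20% v 30% at 75 per arm: SE0 = √(2 × 0.1875/75) = 0.0707, SE1 = √(0.37/75) = 0.0702, (0.10 − 0.1386)/0.0702 = −0.549, and Φ = 0.291.

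**Step 2: precision when observed risks are equal.** Upper 95% risk-ratio limit = exp[1.96·√(2(1−p)/(np))]. Risk-difference half-width = 1.96·√(2p(1−p)/n).

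| UC risk | Per arm | Power, +10 points | Upper risk-ratio limit | Half-width, points |
|---|---|---|---|---|
| 20% | 56 | 22.9% | 2.10 | 14.8 |
| 25% | 56 | 20.9% | 1.90 | 16.0 |
| 30% | 56 | 19.6% | 1.76 | 17.0 |
| 20% | 75 | 29.1% | 1.90 | 12.8 |
| 25% | 75 | 26.5% | 1.74 | 13.9 |
| 30% | 75 | 24.8% | 1.63 | 14.7 |

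Exact enumeration of the binomial likelihood ratio test at 75 per arm gives 30.3%, 27.2% and 25.4%, close to the normal approximation.

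**Step 3: a non-significant excess.** Suppose 19 of 75 UC patients (25.3%) and 30 of 75 PHIT patients (40.0%) are affected.
- Expected counts under equality are 24.5 affected and 50.5 unaffected per arm. G² = 2·[19 ln(19/24.5) + 30 ln(30/24.5) + 56 ln(56/50.5) + 45 ln(45/50.5)] = 3.69 on 1 df, p = 0.055.
- Risk ratio 30/19 = 1.58. SE of the log ratio = √(1/19 − 1/75 + 1/30 − 1/75) = 0.2435, so the 95% CI is 0.98 to 2.54.
- Risk difference +14.7 points, SE 7.56 points, 95% CI −0.2 to +29.5.

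The test alone reads as no significant difference. The interval shows that a 2.5-fold rise is not excluded.

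**Step 4: could a margin be tested?** For a 10-point margin with equal true risks, one-sided 2.5% and 80% power, n per arm = (1.96 + 0.8416)² × 2p(1−p)/0.10². This gives 252, 295 and 330 at 20%, 25% and 30%, against 75 enrolled.

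**The case against.** The plan commits to estimating rates in each arm, so the example above would be published as 25% v 40%, and a reader could form an interval from the counts. This stands: a reader might infer that an excess would be hidden, but the documents do not support that. What is missing is its stated uncertainty.

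A reader might also infer that the sponsor means to take non-significance as proof of equal safety. No passage says so, and section F rests the trial's significance conclusion on the gait speed test alone. The point is narrower: the planned test could not support the safety claim, and no other comparison is planned.

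A third inference is that the test would have an inflated false-positive rate because one person can have several events. Repeats are realistic: in the Phase II pilot (section D1.4), "6 episodes (over 2 individuals) were reported in the UC group". But the plan names no event model, and a likelihood ratio test within a negative binomial model would fit its wording. The fair statement is that handling of repeats is unspecified.

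The plan names no confidence interval for any outcome, so the request may look like general reporting practice. It weighs more here because a no-worse claim depends on the interval.

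Two cautions on the data also stand. One of the seven script contacts is at baseline, leaving six during follow-up. The script's listed examples do not name falls, although the list is not exhaustive.

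**Conclusion.** The point holds as a gap between the aim and its analysis. The safety part of Aim 1 and Hypothesis 1.1 is a no-worse claim; the planned test cannot support it when non-significant, and no between-arm interval is planned to say what excess is excluded.

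Under the re-hospitalisation assumption of 20-30%, a true 10-point rise would be detected only about 20-29% of the time across 56 to 75 per arm. Equal observed risks would still leave an upper risk-ratio limit between about 1.6 and 2.1. These figures illustrate one event type, treated as yes/no over an unstated horizon; they say nothing about falls or emergency visits.

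A reader might infer that the trial is too small or must adopt a formal margin. That does not follow: the documents size the trial for gait speed, that calculation reproduces, and a modestly worded safety aim needs no margin. This is a cheap improvement, and the efficacy analysis is untouched.

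**What to change.** In section F, replace the adverse event sentence with text such as:

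> For each adverse event type we will report the rate in each arm and the PHIT/UC rate ratio with 95% CI, from a model that allows for repeat events in one person (Poisson with robust variance, or negative binomial) with a person-time offset. We will also report the risk difference with 95% CI for at least one event. All enrolled participants are analysed by assigned arm. An event that leads to withdrawal is counted, and person-time ends at the last date with adverse event information. A non-significant comparison will not be taken as evidence of equal safety.

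State the time window as well: Hypothesis 1.1 is worded at 60 days, while the script runs to day 180. Nursing home days are a duration and can be summarised separately by arm.

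Reword the safety part of Aim 1 and Hypothesis 1.1 to: estimate the difference in adverse event rates between PHIT and UC. No margin is proposed, because one of 10 points would need about 252-330 per arm.

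The cost is wording. The analysis uses adverse event contacts already planned and needs no extra patients or visits; events after a withdrawn participant's last contact remain unobserved, as now. The downside is a more modest safety claim and somewhat wider intervals when events repeat. For example, with 75 per arm, 25% affected and two episodes each (37.5 events per arm), the upper limit at equal rates is exp[1.96·√(2/37.5)] = 1.57 if episodes are treated as independent. It is exp[1.96·√(2 × 0.75/(75 × 0.25))] = 1.74 if clustering within person is allowed for.
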